2.1.1 General definitions

All procedures, including randomization of participants, and data collection are to be done at Visit 1, and baseline in this document refers to the data collected during Visit 1.

2.2 Analysis sets

The data obtained from this study will be analyzed for the full analysis set (FAS) and perprotocol set (PPS). The efficacy analysis will be performed using the FAS and PPS and the primary efficacy population is the FAS.

- The FAS will consist of randomized participants who had assessment for the primary endpoint.
- The PPS will consist of participants in the FAS who completed the study without major protocol deviations. Major protocol deviations include: PsA not evaluated by EARP or investigator, primary endpoint (CASPAR) not evaluated, deviation from the inclusion/exclusion criteria, randomization error, and other cases that could be considered major protocol deviations.

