6.3 Blinding

Assigned group will be open to participants, investigator staff, persons performing the assessments and the Novartis clinical trial team (CTT). Such that no aggregate statistical analyses by treatment shall be performed prior to the database lock.

7 Informed consent procedures

Eligible participants may only be included in the study after providing (witnessed, where required by law or regulation), Institutional Review Board (IRB)-approved informed consent.

In cases where the participant's representative(s) gives consent, the participant must be informed about the study to the extent possible given his/her level of understanding. If the participant is capable of doing so, he/she must indicate agreement by personally signing and dating the written informed consent document.

Informed consent must be obtained before conducting any study-specific procedures (e.g. all of the procedures described in the protocol). The process of obtaining informed consent must be documented in the participant source documents.

Novartis will review the Contract Research Organization (CRO) proposed ICF to ensure it complies with the International Council for Harmonization of Technical Requirements for Pharmaceuticals for Human Use (ICH) E6 Good Clinical Practice (GCP) guidelines and regulatory requirements and is considered appropriate for this study. Any further changes to the proposed consent form suggested by the investigator must be agreed to by Novartis before submission to the IRB.

8 Visit schedule and assessments

The assessment schedule (Table 8–1) lists all of the assessments when they are performed. All data obtained from these assessments must be supported in the participant's source documentation.

All baseline assessments may occur during the screening, and all procedures for each participant is performed for one day (Visit 1). If an additional time is required depending on the circumstances of the institution and so on, the data specified in this study protocol are recommended to be collected as soon as possible.

Participants should be seen for all assessments as outlined in the assessment schedule (Table 8–1).

Table 8–1 Assessment schedule

Period	Screening	Randomization	Intervention	Physical examination	Evaluation
Visit Name	Visit 1				
Day/Week/Month	Day 1				
Obtain informed consent ¹⁾	X				
Demographics	Year of birth, age	X			
	Sex	X			
	Height (cm)	X			
	Weight (kg)	X			
	Body Mass Index (BMI)	X			
	Alcohol consumption status	X			

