8.5.1 Primary endpoint

The primary endpoint of this study is detection rate of PsA. The assessments are measured by the CASPAR including clinical assessment, radiography and blood test. In addition, some values which are included the CASPAR are replaced by the values in Section 8.2.

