8.5.1.1 CASPAR

In this study, the CASPAR will be measured for all participants after the EARP questionnaire evaluation and the investigator's judgement are completed in each group. The details of the CASPAR scoring are in the Table 8-2 (Cantini F, et al. 2010).

Table 8-2 CASPAR score

To meet the CASPAR, a patient must have an inflammatory articular disease (inflammatory joint (peripheral) disease, enthesitis, or inflammatory axial disease) with ≥ 3 points from the above criteria.

Criteria	Point
Current PsO	2
Personal history of PsO	1

To meet the CASPAR, a patient must have an inflammatory articular disease (inflammatory joint (peripheral) disease, enthesitis, or inflammatory axial disease) with ≥ 3 points from the above criteria.

Criteria	Point
Family history of PsO	1
Typical PsO nail dystrophy (onycholysis, pitting, hyperkeratosis)	1
Current dactylitis or history of dactylitis	1
Negative rheumatoid factor	1
Hand and foot plain radiography (evidence of juxta-articular new bone formation in hand (including wrist) and feet (including ankle))	1

The items for the CASPAR measurement are as follows.

- Clinical assessment

Inflammatory joint disease (presence or absence of Inflammatory joint (peripheral) disease, enthesitis and inflammatory axial disease), date of diagnosis for PsO[#], family history of PsO[#], presence or absence of typical psoriatic nail dystrophy (onycholysis, pitting, hyperkeratosis), presence or absence of dactylitis, history of dactylitis
- Blood test

Rheumatoid factor
- Radiography

Hand and foot plain X-ray (evidence of juxta-articular new bone formation in hand (including wrist) and feet (including ankle))

Note) #: These values which are included the CASPAR are replaced by the values in Section 8.2.2.2.

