12.1 Analysis sets

The data obtained from this study will be analyzed for the full analysis set (FAS) and per-protocol set (PPS). The efficacy analysis will be performed using the FAS and PPS and the primary efficacy population is the FAS.

- The FAS will consist of all patients as randomized who had assessment for the primary endpoint.
- The PPS will consist of all patients in the FAS who completed the study without major protocol deviations.

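### The full analysis set depends on CASPAR, so screen-negative participants without CASPAR leave the primary denominator although their outcome (not detected) is already known, and no planned analysis brings them back

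*SAP*

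**What the plan says.** Both documents condition the full analysis set (FAS) on the primary endpoint assessment. SAP 2.2: "The FAS will consist of randomized participants who had assessment for the primary endpoint". Protocol 12.1: "The FAS will consist of all patients as randomized who had assessment for the primary endpoint".

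Protocol 8.5.1 says what that assessment is: "The assessments are measured by the CASPAR including clinical assessment, radiography and blood test". SAP 2.2 also equates the primary endpoint with CASPAR, in its list of major deviations for the per-protocol set (PPS).

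The detection rate (Protocol 2 and 12.4.1; SAP 1.2 and 2.4.1) is the number of true positives over all subjects in the arm, with formula TP/(TP+FP+TN+FN). A true positive must be screen-positive (EARP of 3 or more, or suspected by the investigator) and have CASPAR of 3 or more. The screen comes first: under Protocol 8.5.1.1, "the CASPAR will be measured for all participants after the EARP questionnaire evaluation" and the investigator's judgement.

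On missing data, SAP 2.1 rules out imputation and uses available data. Protocol 12.4.3 plans no sensitivity analysis. The only further primary analysis is on the PPS (SAP 2.4.3), which is a subset of the FAS. SAP 2.3.1 and 2.3.3 tabulate losses and reasons by group without re-estimating the rate.

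**The concern.** The endpoint is a conjunction, so a negative screen settles it: the participant is TN or FN, and neither is a detection. Requiring CASPAR for entry to the FAS discards people whose primary outcome is known, from a denominator described as all subjects. The same rule discards screen-positives without CASPAR, whose outcome really is unknown.

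The result of the screen is known before CASPAR is done, and CASPAR needs blood and X-ray. Protocol 8 foresees that not everything will be finished on the day: "If an additional time is required depending on the circumstances of the institution and so on", the remaining data are to follow as soon as possible. Protocol 6.3 adds: "Assigned group will be open to participants, investigator staff, persons performing the assessments". Completion of CASPAR could therefore depend on the screen result, and differently in the two arms. At stake are the size of the reported difference and, in a close result, the superiority claim, which rests on the lower confidence limit being above 0.

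**Working it through.** **Inputs.** Detection rates 9% (Routine practice) and 19.7% (EARP), 184 per arm, 10% allowance for invalid cases, two-sided 0.05 (Protocol 12.7, SAP 3). Superiority if the lower 95% limit exceeds 0 (SAP 2.4.2). Assumed: an unpooled Wald interval, since the SAP names no method; the numbers lost; and the screen-positive shares.

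**1. The plan's own figure.** (1.96 + 0.842)² × (0.09 × 0.91 + 0.197 × 0.803) / 0.107² = 164.64, so 165 per arm; 165/0.9 = 183.3, so 184 per arm and 368 in total. This reproduces and is not affected by the point.

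**2. Screen-negatives lost.** Dropping k of them changes TP/N to TP/(N − k), which is never lower. With k = 5: 19.7% × 184/179 = 20.3%. If both arms lose 5, the difference of 10.7 points becomes 10.7 × 184/179 = 11.0.

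**3. Effect on the claim.** Exact enumeration of both binomials. False superiority is the chance of claiming EARP superior under equal true rates (nominal 2.5%), over common rates of 9% to 19.7%:

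| Screen-negatives lost (EARP, Routine) | False superiority |
|---|---|
| 0, 0 | 2.6% |
| 1, 0 | 2.7% |
| 3, 0 | 2.8–3.1% |
| 5, 0 | 3.0–3.5% |
| 5, 3 | 2.7–2.9% |
| 5, 5 | 2.6% |
| 18, 0 (extreme bound) | 4.9–6.9% |

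Power at 19.7% against 9%: 84.8% with no loss, 82.2% with 5 lost in Routine only, and 73.8% with 18 lost in Routine only (extreme bound).

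**4. A close result.** 29/184 against 17/184 has a lower limit of −0.20 points. Dropping 4 EARP screen-negatives (29/180) moves it to +0.06. Conversely, 30/184 against 17/184 has +0.28; dropping 5 Routine screen-negatives (17/179) moves it to −0.04. No detection changes in either case.

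**5. Screen-positives lost.** The direction depends on whom is lost. With 17/184 = 9.24%, dropping 5 who would have been CASPAR-negative gives 17/179 = 9.50%, a rise. If loss is unrelated to CASPAR among screen-positives, the rate falls on average: with a screen-positive share of 30%, (0.09 × 184 − 5 × 0.09/0.3)/179 = 8.4%. By simulation, 5 screen-positives lost in Routine only give false superiority of 4.0–5.4% at a Routine screen-positive share of 30%, and 3.1–3.6% at 50%.

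**6. Loss unrelated to screen result and PsA.** Numerator and denominator shrink in proportion, so there is no bias.

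**The case against.** CASPAR is required for everyone, and SAP 2.1.1 says: "All procedures, including randomization of participants, and data collection are to be done at Visit 1". A partly completed CASPAR can often be resolved, because Protocol 8.5.1.1 states: "To meet the CASPAR, a patient must have an inflammatory articular disease". Without such disease, X-ray and rheumatoid factor are irrelevant. Loss may therefore be very small, and step 3 shows that 1 to 3 lost in one arm, or equal loss in both, hardly changes the error rate. All of this stands, and it limits the severity.

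It can also be said that the wording does not clearly exclude these people. SAP 2.2 lists a missing CASPAR as a deviation that removes FAS members from the PPS, which is either redundant or implies that some FAS members lack CASPAR. That ambiguity is real but does not rescue the denominator: every cell of TP/(TP+FP+TN+FN) is defined by a CASPAR result, and the available-data rule would still leave these people out.

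Finally, a reader could divide the reported true positives by the number randomised. That treats undetermined cases as not detected, so it gives only a lower bound per arm, and the screen results of those excluded are not promised.

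A reader might infer that the rule favours EARP or inflates the false-positive rate to 5–7%. The documents do not support this. The effect can go either way, and those figures need the whole 10% allowance to be screen-negatives lost from one arm with none lost from the other. That allowance is a sample-size margin, not a forecast of missing CASPAR. Nor may one infer that losing screen-positives always lowers a rate (step 5).

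**Conclusion.** The point holds. As written, the primary denominator omits screen-negatives without CASPAR, who are known non-detections under the plan's own definition, and nothing planned restores them. The rate of an arm that loses them is never understated by that loss. The difference is distorted when loss depends on the screen result, and false superiority rises only when that loss is unequal between arms.

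The size is unknown. With 5 lost in one arm the effect is modest: false superiority of 3.0–3.5% instead of 2.6%, or power of 82.2% instead of 84.8%, still above the planned 80%. These figures rest on the assumed Wald interval and assumed losses; those for screen-positives also depend strongly on the assumed screen-positive share. Severity is low to moderate: a cheap safeguard for the primary result, not evidence that the result will be biased.

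**What to change.** 1. Add to SAP 2.4.3 an analysis of the detection rate on all randomised participants. Known non-detections count as not detected: screen-negatives with or without CASPAR, and unscreened participants with a negative CASPAR. Undetermined cases (screen-positive without CASPAR; unscreened with CASPAR positive or missing) are set to detected or to not detected separately by arm, giving four combinations. Each undetermined participant moves an arm by 1/184 = 0.54 points, so 5 per arm span 10/184 = 5.4 points in the difference.

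2. If the primary analysis is changed too, keep screen-negatives without CASPAR in the denominator, but do not at the same time simply drop screen-positives without CASPAR. With 10% of screen-positives lost, unrelated to CASPAR, that would turn 19.7% into 0.197 × 0.9/(1 − 0.1s) = 18.3% (screen-positive share s = 0.3) or 18.7% (s = 0.5). Instead estimate each arm as s × q, where q is the share with CASPAR of 3 or more among the m screen-positives with CASPAR, with variance q²s(1 − s)/N + s²q(1 − q)/m. In simulation, with 5 screen-positives lost in Routine, this held false superiority at 2.6–2.7%. State that it assumes CASPAR is missing at random among screen-positives, and that unscreened participants are handled in item 1.

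3. Reconcile the CASPAR item in the PPS deviation list with the FAS definition in Protocol 12.1 and SAP 2.2. Keep the set with both screen and CASPAR for sensitivity, specificity, PPV and NPV.

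The cost is some wording, one extra table from data already collected, and a slightly longer variance if item 2 is adopted. If no CASPAR is missing, the results are unchanged.

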2.3 Patient disposition, demographics, and other baseline characteristics

2.3.1 Patient disposition

For randomized participants, the numbers and percentages of participants by randomization, whether PsA was evaluated by EARP or investigator, whether the study was completed, and the reason for not completing the study, will be presented by group and overall.

A separate list of participants who did not complete the study will be presented with the participant number, institution, group, sex, age, date of informed consent, and reason for study discontinuation.

Additionally, a separate list of screen failures will be presented with the participant number, institution, group, sex, age, date of informed consent, and reason for screen failure.

2.3.2 Protocol deviations and analysis restrictions

For randomized participants, the numbers and percentages of participants who had at least one major protocol deviation, both overall and for each category, will be presented by group and overall.

A separate list of participants with a major protocol deviation will be presented with the participant number, institution, group, sex, age, date of informed consent, whether the study was completed, and description of the major protocol deviation.

2.3.3 Disposition by analysis set

For randomized participants, the numbers and percentages of participants in the FAS and PPS and the reason for exclusion from the FAS and PPS will be presented by group and overall.

2.3.4 Demographics and other baseline characteristics

2.3.4.1 Demographic characteristics

Demographic characteristics will be analyzed for the FAS and will include the following parameters:

- Age (year): using the age data recorded in the CRF
- Age category (year): <65 years old, ≥65 years old
- Sex: Male, Female
- Height (cm)
- Weight (kg)
- Body mass index (BMI, kg/m²): using the BMI data recorded in the CRF
- Drinking history: Current drinker, Former drinker, Never drinker
- Smoking history: Current smoker, Former smoker, Never smoker

English SAP Version 01 (release date: 15Jun2023)

Descriptive statistics will include the number of participants, mean, standard deviation, median, minimum, and maximum for continuous variables, and the number and percentage of participants for categorical variables.

Statistical significance for differences between the two groups will be tested by Independent ttest or Wilcoxon rank sum test for continuous data, and by Chi-square test or Fisher's exact test for categorical variables.

2.3.4.2 PsO related characteristics

PsO related characteristics will be analyzed on the FAS and will include the following parameters:

- Duration of PsO (month): (date of informed consent date of PsO diagnosis + 1) / 30.4375
 - o If the month or day of PsO diagnosis is missing, January or day 1 will be imputed.
 - o If the year of PsO diagnosis is missing, the date of diagnosis will be considered missing, as is the duration of disease, which will be therefore excluded from analysis.
- PASI score
- PASI categories: 10-20 (moderate), >20 (severe)
- PASI categories: 10-11, 12-13, 14-15, 16-17, 18-19, ≥ 20
- Family history of PsO: Present, Absent
 - o The family history is 'Present' if any of the multiple selections (father, mother, siblings, and others) are checked, and 'Absent' if 'none' is checked.
- Types of PsO family history: Father, mother, siblings, others
 - o Participants with 'Present' for PsO family history will be analyzed; the multiple selections allow for multiple counting.
- Family history of PsA: Present, Absent
 - o 'Present' if any of the multiple selections (father, mother, siblings, and others) are checked, and 'Absent' if 'none' is checked
- Types of PsA family history: Father, mother, siblings, others
 - o Participants with 'Present' for PsA family history will be analyzed; the multiple selections allow for multiple counting.
- Presence or absence of hard-to-treat area involvement: Present, Absent
 - 'Present' if any of the multiple selections for hard-to-treat area involvement (scalp, palmoplantar, and nails) are checked, and 'Absent' if 'none' is checked
- Hard-to-treat area involvement: Scalp, palmoplantar, and nails

- o Participants with 'Present' for hard-to-treat area involvement will be analyzed; the multiple selections allow for multiple counting.
- Musculoskeletal symptoms: Present, Absent
- Nail psoriasis severity index (NAPSI): Scores for each of the left and right hands and left and right feet and their total score
- Number of swollen joints (SJC66)
- Number of tender joints (TJC68)
- Sum of SJC66 and TJC68

Descriptive statistics will include the number of participants, mean, standard deviation, median, minimum, and maximum for continuous variables, and the number and percentage of participants for categorical variables.

Statistical significance for differences between the two groups will be tested by Independent ttest or Wilcoxon rank sum test for continuous data, and by Chi-square test or Fisher's exact test for categorical variables.

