12.5.2 Demographic characteristics and PsO related characteristics

Analysis on the demographic characteristics and PsO related characteristics will be performed on the FAS and PPS and presented by patients with and without PsA.

The following demographic characteristics and PsO related characteristics will be included.

- Demographic characteristics include age, sex, BMI, alcohol consumption status and smoking status.
- PsO related characteristics include duration of PsO, family history of PsO, family history of PsA, PASI score, status of hard-to-treat area involvement (scalp, palmoplantar and nails), status of musculoskeletal symptoms, NAPSI (total), SJC66, TJC68, status of co-morbidities (heart diseases, stroke, diabetes, hyperlipidemia, hypertension and fatty liver), and status of PsO related treatment other than medications.

Continuous variables will be summarized with the number of patients, mean, standard deviation, median, minimum, and maximum and categorical variables will be summarized with the number and percentage of patients. The statistical significance for the differences between two groups is tested using independent t-test or Wilcoxon rank sum test for continuous data and using Chi-square test or Fisher's exact test for the categorical data.

In addition, the number and percentage of patients having at least one prior and ongoing PsO related treatment other than medications will be tabulated by system organ class and preferred term of the MedDRA dictionary. The number and percentage of patients having at least one prior and ongoing medication will be tabulated by therapeutic main group and preferred term of the WHO drug dictionary.

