12.7 Sample size calculation

According to previous studies, the prevalence of PsA among PsO patients in Korea ranged from 9.0% to 14.1% (9.0% in Back HJ, et al. 2000, 10.8% in Oh et al. 2017, 13.5% in Choi et al. 2017, 14.1% in Choi HJ, et al. 2008) (Back HJ, et al. 2000) (Oh EH, et al. 2017) (Choi JW, et al. 2017) (Choi HJ, et al. 2008). Considering that this study excludes patients who have received treatment with biologic DMARDs to reduce any confounding as trying to demonstrate the usefulness of the EARP as an early diagnosis tool for PsA, the detection rate of PsA among patients with PsO is assumed to be 9% in the Routine practice group.

For the EARP group, the detection rate of PsA among PsO patients is assumed to be 19.7%, given that in a recent large meta-analysis of 266 studies worldwide, the overall prevalence of PsA among PsO patients was reported as 19.7% (Alinaghi F, et al. 2019). Several studies and meta-analyses revealed that undiagnosed PsA is common in patients with PsO and between 9% and 13.76% of patients with PsO may have undiagnosed PsA (9% in Sleman et al. 2015, 10.1% in Coates et al. 2016, 12.4% in Mease et al. 2013, 13.76% in Alshaikh et al. 2020) (Spelman L, et al. 2015) (Coates LC, et al. 2016b) (Mease PJ, et al. 2017) (Alshaikh AF, et al. 2020). Thus, it would be a reasonable assumption that the detection rate of PsA among patients with PsO will increase to 19.7% in the EARP group if the EARP screening will improve the detection rate by around 11%.

Based on a two-sided alpha=0.05 and power 1-β=0.80, assuming the PsA detection rates of 9% and 19.7% in the Routine practice and EARP groups, respectively, the sample size of this study is estimated to be about 165 per group.

$$n = \frac{(Z_{\alpha/2} + Z_{\beta})^2 (P_C * (1 - P_C) + P_I * (1 - P_I))}{(P_C - P_I)^2} = \frac{(1.96 + 0.842)^2 (0.09 * (1 - 0.09) + 0.197 * (1 - 0.197))}{(0.09 - 0.197)^2} = 164.64$$

Considering 10% of invalid cases, a total of 368 patients (184 patients per group) is planned to be enrolled in this study.

13 Ethical considerations and administrative procedures

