2.1 Data analysis general information

All analyses will be performed by a designated Contract Research Organization (CRO) using the SAS software (Version 9.4).

Descriptive statistics will include the number of participants, mean, standard deviation, median, minimum, and maximum for continuous variables, and the number and percentage of participants for categorical variables. If necessary, more detailed information will be provided. For continuous data, statistical significance for differences between the two groups will be tested by Independent t-test if normality is met, or Wilcoxon rank sum test if normality is not met. For categorical data, statistical significance for differences between the two groups will be tested by Chi-square test. If cells with an expected frequency of <5 exceed 20% of all cells when testing for differences between the groups, Fisher's exact test will used instead of Chi-square test.

All the statistical tests will use a two-sided test at the significance level of 0.05. Statistical summaries will be presented to two decimal places, and p-values to three decimal places.

Prior/concomitant PsO related treatments and other medical history will be coded using the MedDRA (latest version at time of analysis) System Organ Class and Preferred Term and listed in descending order by incidence for the study groups. Prior/concomitant medications will be coded using the WHO Drug Dictionary (latest version at time of analysis) Therapeutic Main Group and Preferred Name and listed in descending order by incidence for the study groups.

Missing data will not be imputed, and all statistical analyses will be performed using available data.

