2.5.2.2 PsO related characteristics with or without PsA

The parameters for PsO related characteristics are identical to the parameters provided in Section 2.3.4.2.

Descriptive statistics will include the number of participants, mean, standard deviation, median, minimum, and maximum for continuous variables, and the number and percentage of participants for categorical variables, presented by the presence or absence of PsA.

Statistical significance for differences between the two groups will be tested by Independent ttest or Wilcoxon rank sum test for continuous data, and by Chi-square test or Fisher's exact test for categorical variables.

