2.7 Interim analysis

No interim analysis is planned for this study.

3 Sample size calculation

According to previous studies, the prevalence of PsA among PsO patients in Korea ranged from 9.0% to 14.1% (9.0% in Back HJ, et al. 2000, 10.8% in Oh et al. 2017, 13.5% in Choi et al. 2017, 14.1% in Choi HJ, et al. 2008) (Back HJ, et al. 2000) (Oh EH, et al. 2017) (Choi JW, et al. 2017) (Choi HJ, et al. 2008). Considering that this study excludes patients who have received treatment with biologic disease-modifying anti-rheumatic drugs (DMARDs) to reduce the effect of any confounding factors as trying to demonstrate the usefulness of the EARP as an

early diagnosis tool for PsA, the detection rate of PsA among patients with PsO is assumed to be 9% in the Routine practice group.

For the EARP group, the detection rate of PsA among PsO patients is assumed to be 19.7%, given that in a recent large meta-analysis of 266 studies worldwide, the overall prevalence of PsA among PsO patients was reported as 19.7% (Alinaghi F, et al. 2019). Several studies and meta-analyses revealed that undiagnosed PsA is common in patients with PsO, ranging from 9% to 13.76% (9% in Sleman et al. 2015, 10.1% in Coates et al. 2016, 12.4% in Mease et al. 2013, 13.76% in Alshaikh et al. 2020) (Spelman L, et al. 2015) (Coates LC, et al. 2016b) (Mease PJ, et al. 2017) (Alshaikh AF, et al. 2020). Thus, it would be a reasonable assumption that the detection rate of PsA among patients with PsO will increase to 19.7% in the EARP group if the EARP screening will improve the detection rate by around 11%.

Based on a two-sided α =0.05 and power 1- β =0.80, assuming the PsA detection rates of 9% and 19.7% in the Routine practice and EARP groups, respectively, the sample size of this study is estimated to be approximately 165 per group.

$$n = \frac{\left(Z_{\alpha/2} + Z_{\beta}\right)^{2} (P_{C} * (1 - P_{C}) + P_{I} * (1 - P_{I}))}{(P_{C} - P_{I})^{2}} = \frac{(1.96 + 0.842)^{2} (0.09 * (1 - 0.09) + 0.197 * (1 - 0.197))}{(0.09 - 0.197)^{2}} = 164.64$$

Considering 10% of invalid cases, a total of 368 patients (184 patients per group) is planned to be enrolled in this study.

4 Change to protocol specified analyses

No analyses changed from the protocol.

5 Reference

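### SAP 2.5.2.2 compares each hard-to-treat area by PsA status only among participants with at least one such area, so each area's percentage depends on the other areas

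*SAP*

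**What the plan says.** SAP 2.3.4.2 lists the psoriasis-related parameters for the FAS. Three of them are breakdowns of a tick-all-that-apply item: type of relative with PsO, type of relative with PsA, and which hard-to-treat area is involved. Each is limited to participants marked Present on the parent item. For areas the rule is "Participants with 'Present' for hard-to-treat area involvement will be analyzed; the multiple selections allow for multiple counting"; for relatives with PsO it is "Participants with 'Present' for PsO family history will be analyzed; the multiple selections allow for multiple counting", and the PsA family-history rule matches. The section closes with one general instruction to test "by Chi-square test or Fisher's exact test for categorical variables". It gives no table layout for multiple-response items.

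SAP 2.5.2.2 carries this into the comparison by PsA status: "The parameters for PsO related characteristics are identical to the parameters provided in Section 2.3.4.2". Under SAP 2.5.2, PsA present means a true positive and PsA absent means everyone else.

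The same SAP list also contains parameters without the restriction: family history of PsO, family history of PsA and any hard-to-treat involvement (each Present/Absent), plus NAPSI by limb and in total.

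On the protocol side, 8.2.2.2 records presence or absence of scalp, palmoplantar and nail involvement, and 12.5.2 lists "status of hard-to-treat area involvement (scalp, palmoplantar and nails") among the characteristics to compare by PsA status.

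**The concern.** Describing PsA against non-PsA patients is a secondary objective. A reader of the area table will want to know whether nail, scalp or palmoplantar disease is more common in those with PsA. The planned percentage answers a different question: among people with at least one involved area, how often is this area one of them? Selection into that denominator depends on the other areas. If scalp disease is more common in one group, that group's denominator grows and its nail percentage falls, although nail disease itself is unchanged.

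The PsA groups are not randomised, so nothing makes the other areas similar between them. Under the current text, scalp, palmoplantar and yes/no nail involvement have no planned comparison on the full analysis set.

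**Working it through.** **Plan's own figures.** The documents give no number for this analysis. Their sample-size figure reproduces and supplies plausible group sizes. Protocol 12.7 works "assuming the PsA detection rates of 9% and 19.7% in the Routine practice and EARP groups, respectively":

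(1.96 + 0.842)² × (0.09 × 0.91 + 0.197 × 0.803) / 0.107² = 164.64, so 165 per group; 165 / 0.90 = 183.3, so 184 per group and 368 in total.

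With 165 evaluable per group, the expected number of true positives is 165 × (0.09 + 0.197) = 47.4. The comparison by PsA status is then about 47 v 283.

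**Formula.** A participant with nails ticked is Present by definition, so P(nails | Present) = P(nails) / P(any area). This needs no independence assumption. For illustration, take the areas as independent within each group, with s = scalp, p = palmoplantar and n = nails:

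P(any area) = 1 − (1 − s)(1 − p)(1 − n).

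**Assumed inputs.** Area prevalences are not in the documents, so a range is shown. Each pair is PsA present v absent; differences are in percentage points, from unrounded values.

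| Nails | Scalp | Palmoplantar (both) | P(any area) | Nails among Present | Difference |
|---|---|---|---|---|---|
| 40% v 40% | 50% v 50% | 15% | 0.745 v 0.745 | 53.7% v 53.7% | 0 |
| 40% v 40% | 70% v 50% | 15% | 0.847 v 0.745 | 47.2% v 53.7% | −6.5 |
| 40% v 40% | 80% v 50% | 15% | 0.898 v 0.745 | 44.5% v 53.7% | −9.1 |
| 60% v 40% | 80% v 80% | 15% | 0.932 v 0.898 | 64.4% v 44.5% | 19.8 |
| 60% v 40% | 60% v 60% | 15% | 0.864 v 0.796 | 69.4% v 50.3% | 19.2 |
| 60% v 40% | 20% v 20% | 15% | 0.728 v 0.592 | 82.4% v 67.6% | 14.9 |
| 60% v 40% | 20% v 20% | 5% | 0.696 v 0.544 | 86.2% v 73.5% | 12.7 |
| 60% v 40% | 80% v 50% | 15% | 0.932 v 0.745 | 64.4% v 53.7% | 10.7 |

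**Odds ratio.** Let q = 1 − (1 − s)(1 − p) in each group. Under independence the odds of nail disease among Present are the full-set odds divided by q. The odds ratio is therefore multiplied by q(absent)/q(present). If scalp and palmoplantar rates match, it is unchanged, and only the percentage difference and the number analysed shrink. With scalp 80% v 50% and palmoplantar 15%, q is 0.83 v 0.575. A true odds ratio of 2.25 (60% v 40%) becomes 2.25 × 0.575/0.83 = 1.56, and a true 1.00 becomes 0.69.

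**Effect on the test.** Simulation at 47 v 283 used 20,000 replicates per case and Pearson Chi-square at two-sided 0.05, without the Fisher fallback.
- Nails equal at 40%, palmoplantar 15%: the Present-only nail test rejects 19% of the time with scalp 80% v 50%, 12% with 70% v 50%, and 5% with equal scalp.
- Nails 60% v 40%, palmoplantar 15%: Present-only power is 41%, 63% and 69% with scalp at 20%, 60% and 80% in both groups. On the full set it is about 73% (normal approximation).

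**Test layout.** Under no difference, one yes/no test per area among Present rejects 0.047 to 0.054 each. One pooled table of all selections rejects 0.050 to 0.051 if selections are mutually exclusive. With overlap it rejects between 0.000 and 0.040 for areas and 0.033 to 0.047 for relatives.

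**The case against.** The strongest reply is that little is lost. The number with nail disease is the same in both denominators, so a reader with the group totals can rebuild the full-set percentage and its 2x2 test. The any-area comparison uses the whole FAS, NAPSI is measured in everyone (Protocol 8.4.1) and compared by PsA status, and the breakdown is openly labelled as conditional. The secondary objective is to describe, and no decision rests on these p-values. The large effects need sizeable scalp differences that the documents do not predict. All of this stands and limits the weight of the point. It does not remove it: NAPSI is a nail severity score and says nothing about scalp or palmoplantar disease, an any-area variable does not give the status of each area, and the printed percentages and p-values remain the conditional ones.

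A departure from the protocol is also not established. Protocol 8.5.2.3 and 12.5.2 can be read as asking for a composite status. The contrast within the SAP is still notable: co-morbidities, worded in parallel in Protocol 12.5.2, are each analysed in SAP 2.3.4.3 on the FAS with a None category.

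**Conclusion.** The point holds for the per-area comparison by PsA status in SAP 2.5.2.2, and in the same form for the breakdown by type of relative. In the cases tried, the planned nail percentages differ by up to 9.1 points when true involvement is equal, and a true 20-point difference shrinks to between 10.7 and 19.8 points. These sizes rest on assumed prevalences and on independence of areas within group. A false difference needs the other areas to differ in frequency by PsA status.

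Four stronger readings are tempting and are not supported.
- Family-history comparisons as a whole are distorted: the Present/Absent comparisons use the full analysis set and are sound.
- The Chi-square test has an inflated error rate: that presumes a pooled multiple-response table, which the SAP does not specify and which was conservative whenever selections overlapped. Separate tests hold about 5% each. The 19% rejection above is a valid test of a conditional quantity that really differs; the fault is the denominator.
- The comparison of randomised arms is biased: the areas are recorded at screening (Protocol Table 8-1), so no systematic difference is expected there.
- The primary result is at risk: the primary analysis, sample size and superiority rule do not use these variables.

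The point is minor.

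**What to change.** In SAP 2.3.4.2, and so in 2.5.2.2, report scalp, palmoplantar, nails and each type of relative as separate yes/no items. Use all participants in the analysis set with data as the denominator, counting a tick of none as no for every item. State that each item gets one 2x2 comparison (Chi-square or Fisher under the existing rule) or no test, and that no Chi-square test is run on pooled multiple-response counts. The breakdown among Present participants can stay as added description.

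The cost is a few sentences of SAP text and a few lines of table programming. No new data are needed.
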